4.1.3 Laboratory data

This section provides further detail on the laboratory parameters that will be listed and summarized as described in [Section 3.2.9.2](#).

Hematology

Hematologic tests include: a complete blood count (CBC) consisting of RBCs, a total white blood cell count (WBC) with differential (total neutrophil [including bands], lymphocyte, monocyte, eosinophil, and basophil counts), hemoglobin, and platelet count.

The following rules will be applied to derive the WBC differential counts when only percentages are available (this is mainly important for neutrophils and lymphocytes, because the CTC grading is based on the absolute counts).

The method to convert the value is straightforward: for each subject, the original lab value (%) is divided by 100 and multiplied by the WBC count, e.g. for neutrophils (NEU):

$$\text{NEU count} = (\text{WBC count}) * (\text{NEU \% value} / 100)$$

In order to derive the corresponding absolute normal range, the rule to be applied depends on the availability of the % range and the absolute range for the differential:

- If % range missing and absolute range missing, then use pre-defined normal range reported in the Merck manual
- If absolute range NOT missing (% range is or isn't missing), then use the absolute range provided by the site
- If % range NOT missing and absolute range missing, then the % normal limits (i.e. LLN and ULN) are divided by 100 and multiplied by the corresponding normal limits of WBC count, e.g. for neutrophils (NEU):

$$\text{LLN for NEU count} = (\text{LLN for WBC count}) * (\text{LLN for NEU \% value} / 100)$$

$$\text{ULN for NEU count} = (\text{ULN for WBC count}) * (\text{ULN for NEU \% value} / 100)$$

Biochemistry

CONFIDENTIAL - For Business Use Only

The following calculation will be applied for corrected calcium in SI unit:

Corrected calcium (mmol/L) = measured total Ca (mmol/L) + 0.02 (40 - serum albumin [g/L]), where 40 represents the average albumin level in g/L.

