6.2.3 Criteria for LDK378 dose modifications

An LDK378 dose reduction will follow the guidelines described in [Table 6-2](#). For each patient, a maximum of 3 dose modifications is allowed after which the patient must be discontinued from treatment with LDK378. Once the dose of LDK378 has been reduced, it cannot be re-escalated. If a patient continues treatment with LDK378 after RECIST-defined PD as determined by the investigator, the criteria for dose modification will also apply.

Table 6-2 Dose reduction steps for LDK378

LDK378 dose levels	Dose* and schedule
Starting dose level	750 qd continuously
Dose level – 1	600 qd continuously
Dose level – 2	450 qd continuously
Dose level – 3	300 qd continuously **

*Dose reduction should be based on the worst preceding toxicity
**Dose reduction below 300 mg/day is not allowed. If a dose reduction below 300 mg/day is required, the patient should be permanently discontinued from LDK378

Guidelines for dose modification and dose interruption of LDK378 are described in [Table 6-3](#).

Table 6-3 Criteria for interruption and re-initiation of LDK378 treatment

Worst toxicity (CTCAE 4.03 Grade)*	Dose Modifications for LDK378
HEMATOLOGICAL	
Neutropenia (ANC)	
Grade 1 (ANC < LLN - $1.5 \times 10^9/L$)	Maintain dose level
Grade 2 (ANC < 1.5 and $\geq 1.0 \times 10^9/L$)	
Grade 3 (ANC < 1.0 and $\geq 0.5 \times 10^9/L$)	
Grade 4 (ANC < $0.5 \times 10^9/L$)	Omit dose until resolved to \leq Grade 2, then: If resolved in ≤ 7 days, then maintain dose level If resolved in > 7 days, then $\downarrow 1$ dose level
Febrile neutropenia (ANC < $1.0 \times 10^9/L$, with a single temperature of $\geq 38.3^{\circ}C$ or a sustained temperature of $\geq 38^{\circ}C$ for more than one hour)	Omit dose until clinically resolved and neutropenia \leq Grade 2, then $\downarrow 1$ dose level
Thrombocytopenia	
Grade 1 (PLT < LLN - $75 \times 10^9/L$)	Maintain dose level
Grade 2 (PLT < 75 and $\geq 50 \times 10^9/L$)	
Grade 3 (PLT < 50 and $\geq 25 \times 10^9/L$)	Omit dose until resolved to \leq Grade 2, then: If resolved in ≤ 7 days, then maintain dose level If resolved in > 7 days, then $\downarrow 1$ dose level
Grade 4 (PLT < $25 \times 10^9/L$)	Omit dose until resolved to \leq Grade 2, then $\downarrow 1$ dose level
HEPATIC	
Alkaline phosphatase and/or Gamma-glutamyl transpeptidase (GGT)	
Isolated elevations of any grade	Maintain dose level

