10.5.3.3 Laboratory abnormalities

For laboratory tests covered by the CTCAE version 4.03, the study's biostatistical and reporting team will grade laboratory data accordingly. For laboratory tests covered by CTCAE, a Grade 0 will be assigned for all non-missing values not graded as 1 or higher. Grade 5 will not be used.

For some cases (e.g. white blood cell differentials), the lower limits of normal ranges used in CTCAE definitions will have to be replaced by a clinical meaningful limit expressed in absolute counts.

For laboratory tests where grades are not defined by CTCAE, results will be graded by the low/normal/high classifications based on laboratory normal ranges.

The following summaries will be generated separately for hematology and biochemistry laboratory tests:

- shift tables using CTCAE grades to compare baseline to the worst on-treatment value
- for laboratory tests where CTCAE grades are not defined, shift tables using the low/normal/high/(low and high) classification to compare baseline to the worst on-treatment value.

All laboratory data will be listed with values flagged to show the corresponding CTCAE grades and the classifications relative to the laboratory normal ranges.

A separate listing will display notable laboratory abnormalities (i.e., newly occurring CTCAE grade 3 or 4 laboratory toxicities).

In addition to the above mentioned tables and listings, other exploratory analyses, for example figures plotting time course of raw or change from baseline in laboratory tests over time or box plots may be specified in the RAP.

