3.1.5 General statistical methodology

3.1.5.1 Multiple assessments within post-baseline visits

If there are multiple measurements/samples within the same post-baseline visit, the last measurement/sample within the visit (sorted by date and as available by time or repeat measurements) will be used in the analysis by visit or overall. For any analyses regarding abnormal assessments or analyses based on worst (or best in the case of ECOG status) post-baseline value (laboratory, ECGs, vital signs, ECOG performance status), all post-baseline values will be included (scheduled, unscheduled, repeat). For any other analyses, only scheduled visits will be included. All unscheduled and repeat measurements will be included in listings.

Laboratory Data

For laboratory data, assessments can be collected from both local and central laboratory on the same date. For shift tables using Common Terminology Criteria (CTC) v4.03 grades to compare baseline to the worst post-baseline value, the assessment with worst post-baseline value is used for analyses irrespective of the source. For Liver function test (LFT) summaries, where concurrent measurements are used in the calculation of number and percentage of patients with worst post-baseline values, the assessment with worst post-baseline value is used (since worst values are based on the largest ratio of lab value to its ULN for each patient) although the worst values for the different parameters may be coming from different laboratories.

12-lead ECG assessments

For all patients, triplicate ECGs are targeted to be measured at the protocol-defined (nominal) time-points. If any patient had more than one measurement at a specific time point, the average of all available measurements (only scheduled one) associated with the nominal time point will be used for the analyses.

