3.2.9.2 Laboratory data

For laboratory data assessments, data from all sources (central and local laboratories) will be combined. The summaries will include all laboratory assessments collected no later than 30 days after study drug discontinuation. All laboratory assessments will be listed and those collected in post-treatment period will be flagged in the listings.

Laboratory data will be classified (by Novartis Oncology Statistical programming) into CTC grades according to the NCI CTCAE v4.03. For all reports, CTC grade is always obtained on the converted measurement in SI unit. The CTC grade 0 will be assigned as below in different scenarios:

- For lab parameters defined by criteria based on normal range only, a severity grade of 0 will be assigned when the value is within normal limits.
- For lab parameters whose grade is defined by criteria based on normal range and absolute values (e.g. platelet count decrease). A severity grade of 0 will be assigned when the value is within normal limits.
- For lab parameters whose grade is defined by criteria based on normal range and the change from baseline value, with no other associated clinical criteria such as concomitant medication (e.g. creatinine increased), the following will be applied. For the baseline grading and for the grading of post-baseline lab values with missing baseline grading, the grade will be derived using the criteria based only on the normal range as per CTCAE v4.03.

A severity grade of 0 will be assigned when the post-baseline value is \leq ULN (for hyper) or \geq LLN (for hypo).

- For CTC grades of glucose (fasting or non-fasting), glucose fasting values will be used. For glucose non-fasting values, Grade 1 or 2 will be reassigned to Grade 0.

Grade 5 will not be used. Parameters for which a grading does not exist will be classified into low/normal/high group by means of laboratory normal ranges.

The following summaries will be produced for the hematology and biochemistry laboratory data (by laboratory parameter):

- Shift tables using CTC grades to compare baseline to the worst post-baseline value for laboratory parameters with CTC grades
- Shift tables using low, normal, high (as well as low and high combined) classifications to compare baseline to the worst post-baseline value for laboratory parameters where CTC grades are not defined.

The following lab parameters will be summarized:

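### When a laboratory supplies only a % range, SAP 4.1.3 multiplies lower limit by lower limit and upper by upper, giving too wide an absolute range for WBC differentials and under-grading some low counts

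*SAP*

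**What the plan says.** SAP 4.1.3 (Hematology) converts percentage differentials to absolute counts and then needs an absolute normal range. It has three tiers:

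- Absolute range available: "then use the absolute range provided by the site".
- Neither range available: "then use pre-defined normal range reported in the Merck manual".
- "If % range NOT missing and absolute range missing": "the % normal limits (i.e. LLN and ULN) are divided by 100 and multiplied by the corresponding normal limits of WBC count". The lower limit becomes LLN(WBC) x LLN(%)/100 and the upper limit ULN(WBC) x ULN(%)/100.

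SAP 3.2.9.2 turns the range into a grade. For parameters graded on the normal range alone, "a severity grade of 0 will be assigned when the value is within normal limits", and the next bullet repeats this for parameters graded on the normal range plus absolute values, which is the structure of the neutrophil grades in protocol Table 6-3. Central and local results are pooled, and for the CTC shift tables SAP 3.1.5.1 says "the assessment with worst post-baseline value is used for analyses irrespective of the source".

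Protocol 10.5.3.3 works in the other order: grade 0 goes to non-missing values that have not already received grade 1 or more. It adds that in some cases, with WBC differentials as the example, "the lower limits of normal ranges used in CTCAE definitions will have to be replaced by a clinical meaningful limit expressed in absolute counts". SAP 4.1.1, on differences between SAP and protocol, is marked as not applicable.

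**The concern.** Multiplying the two lower limits describes a person whose total count and whose percentage both sit at the bottom of their ranges. That is much rarer than 1 in 40, so the derived lower limit is too low; by the same argument the derived upper limit is too high. The tiers are also oddly ordered: a laboratory that reports nothing is given an absolute reference range, while one that reports a % range is given a constructed range that is too wide.

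At stake is the grading of low neutrophil and lymphocyte counts in the safety tables, and safety is a primary objective. The same count could be graded differently only because of how the laboratory reports its limits. Differentials without CTC grades go into low/normal/high shift tables and would lose abnormal values at both ends.

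**Working it through.** **Inputs from the documents.** The product formula and the condition for using it (SAP 4.1.3). Neutrophil grades in x10^9/L (protocol Table 6-3): grade 1 runs from the LLN down to 1.5, grade 2 is below 1.5 down to 1.0, grade 3 is below 1.0 and grade 4 below 0.5. Only the upper edge of grade 1 depends on the LLN. Scheduled hematology is analysed centrally, with local unscheduled testing allowed (protocol 7.2.2.5).

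**Assumed inputs.** The documents give no WBC or % reference range and no numeric derived range, so there is no plan figure to reproduce. I used WBC 4-10 or 3.5-9.5 x10^9/L; neutrophils 40-70%, 40-75% or 50-70%; lymphocytes 20-40%, 20-50% or 15-45%. Each range is read as a central 95% interval, with WBC log-normal and the percentage normal.

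**Step 1: the derived lower limit for neutrophils.**

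- 4.0 x 40/100 = 1.60
- 4.0 x 50/100 = 2.00
- 3.5 x 40/100 = 1.40
- 3.5 x 50/100 = 1.75

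**Step 2: comparison with the range of the count itself.** I simulated WBC x %/100, took its 2.5th and 97.5th percentiles, and found the share of values below the derived LLN (nominally 2.5%).

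| Assumed ranges | Correlation | Product range | Simulated 95% range | Width ratio | Share below derived LLN |
|---|---|---|---|---|---|
| WBC 4-10, neutrophils 40-70% | 0 | 1.60-7.00 | 2.00-5.85 | 1.40 | 0.3% |
| WBC 3.5-9.5, neutrophils 40-75% | 0 | 1.40-7.12 | 1.79-5.86 | 1.41 | 0.3% |
| WBC 3.5-9.5, neutrophils 40-75% | 0.4 | 1.40-7.12 | 1.61-6.39 | 1.20 | 1.0% |
| WBC 4-10, neutrophils 50-70% | 0.4 | 2.00-7.00 | 2.18-6.51 | 1.15 | 1.2% |
| WBC 4-10, lymphocytes 20-40% | 0 | 0.80-4.00 | 1.03-3.26 | 1.43 | 0.3% |
| WBC 4-10, lymphocytes 20-40% | 0.4 | 0.80-4.00 | 0.93-3.58 | 1.21 | 1.0% |

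The width ratio is (product upper - product lower) / (simulated upper - simulated lower); in the second row, (7.12 - 1.40) / (5.86 - 1.79) = 5.72 / 4.07 = 1.41. Over all 12 pairs of ranges, at correlations 0 and 0.4, the ratio is about 1.15 to 1.45 and the share below the LLN about 0.3% to 1.2%. With correlations from -0.3 to 0.5 the ratio spans 1.12 to 1.75 and the share 0.06% to 1.45%. The product range was the wider one in every scenario.

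**Step 3: effect on grade.** With a derived LLN of 1.60, the grade 1 band for neutrophils is 1.50 to 1.59. With the simulated lower limit of 2.00 it would be 1.50 to 1.99. Counts from 1.60 to 1.99 therefore move from grade 1 to grade 0.

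The derived LLN drops below 1.5 when LLN(%) is under 1.5/4.0 = 37.5% (WBC limit 4.0) or under 1.5/3.5 = 42.9% (WBC limit 3.5). With 3.5 x 40% = 1.40, the grade 1 band is empty and counts of 1.40 to 1.49 lie inside the range. SAP 3.2.9.2 as worded makes them grade 0; Table 6-3 makes them grade 2. Under the grading order in protocol 10.5.3.3 they could not be grade 0.

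The lowest neutrophil LLN derived is 1.40, above the grade 3 and grade 4 cut-points, so those grades do not move.

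**The case against.** The strongest reply is that this is a fallback with little reach. Scheduled hematology is central, so the rule touches mainly local, unscheduled results that come with a % range and no absolute range, and nothing in the documents shows that any exist. A patient's worst grade changes only if such a result is that patient's worst. Grade 3-4 neutropenia uses fixed cut-points, Table 6-3 prescribes the same action for grades 1 to 3 neutropenia, and all laboratory values are listed. All of that stands, and it limits the size of the point.

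It can also be said that the SAP grades by CTCAE v4.03, so a fixed grade 2 cut-point would be applied first. A programmer might do that, but the SAP does not state the order, and its grade 0 bullet read literally gives the other result. Three of the four neutrophil limits in step 1 are above 1.5, so the grade 2 overlap is a special case.

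A reader might infer that the SAP breaks a specific protocol limit. The documents do not support that. The protocol sentence applies to some cases, concerns lower limits only and gives no number, so the accurate statement is that it has not been implemented. A reader might also infer that the ranges are far too wide. The direction held in every scenario tried, but the size rests on assumed reference ranges and shrinks as the correlation rises.

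**Conclusion.** The rule is wrong as written, not merely short of detail: whenever it is used under the assumptions tried, it gives a lower limit that is too low and an upper limit that is too high. The excess width is about 15% to 45% for correlations of 0 to 0.4. For neutrophils the loss is mainly grade 1, with a small overlap into grade 2 when the derived limit is below 1.5. The lymphocyte effect on grade cannot be sized, because the documents give no lymphocyte cut-points, and there is no figure for monocytes, eosinophils or basophils.

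Two mismatches with protocol 10.5.3.3 do not depend on those assumptions. The SAP words the grade 0 rule differently, and it names no clinically meaningful absolute lower limit for WBC differentials, while SAP 4.1.1 declares no difference.

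It would go too far to say that severe neutropenia is hidden or that dosing decisions are affected: the serious grades and the Table 6-3 actions rest on fixed cut-points. The number of results affected is unknown from the documents.

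**What to change.** 1. Delete the product bullet in SAP 4.1.3. When the site's absolute range is missing, use one fixed absolute range for grading and shift tables: the central laboratory's, or the Merck manual range the SAP already names.
2. State in SAP 3.2.9.2 that fixed CTCAE cut-points are applied first and that grade 0 goes only to values left ungraded, as in protocol 10.5.3.3.
3. Align SAP 4.1.1 with protocol 10.5.3.3: either state the absolute lower limit used for WBC differentials, or record the departure.

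The cost is one bullet, one sentence on grading order and a lookup change in the programs. The downside is that slightly more grade 1-2 differential abnormalities will be reported. Neither document contains the Merck manual or central limits, so which of the two suits a given site better cannot be judged here; either would grade affected results consistently.

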4.1.4 Last contact date

The last contact date is used for censoring in the OS analyses and will be derived for patients not known to have died at the analysis cut-off using the latest complete date among the following:

- All patient assessment dates (blood draws (laboratory, PK), vital signs, performance status, [REDACTED], ECG, tumor assessments)
- Start and end dates of antineoplastic therapies administered after study treatment discontinuation.
- AE start and end dates
- Last date of contact collected on the 'Survival information' eCRF (do not use if answer to question 'Is subject alive ?' is 'Unknown')
- Study drug start and end dates
- Date of discontinuation on the 'End of Treatment Phase Disposition' and/or the "End of post-treatment phase disposition" eCRFs.

Only dates associated with patient visits or actual examinations of the patient will be used in the derivation. Dates associated with a technical operation unrelated to patient status such as the date a blood sample was processed will not be used. Assessment dates after the cutoff date will not be applied to derive the last contact date.

4.1.5 Month derivation

For all derivations, a month will be calculated as $(365.25 / 12) = 30.4375$ days. If duration is to be reported in months, duration in days will be divided by 30.4375.

4.1.6 Dose interruptions and dose changes

This section provides additional details to those included in [Section 3.1.1.4](#).

All calculations of dose interruptions and dose changes are based on the dose actually taken by the patient.

An interruption is defined as a 0 mg dose taken on one or more days. What follows defines how dose interruptions will be counted in the case of multiple dose interruptions.

- For the first 15 patients who are planned to receive a single dose on the first day of the PK run-in period, the rest four days of PK run-in period will not be counted as an interruption.
- If an interruption occurs consecutively for at least two days due to the same reason, then it will be counted only once (*example: If the actual dose on days 1-3 is 750 mg and actual dose on days 4-5 is 0 mg and dose interruption on days 4-5 is due to AE, then the total number of dose interruptions is 1*).
- If an interruption occurs consecutively for at least two days due to different reasons, then it will be counted for each reason (*example: If the actual dose on days 1-3 is 750 mg and*

actual dose on days 4-5 is 0 mg and dose interruption on day 4 is due to AE and dose interruption on day 5 is due to dosing error, then the total number of dose interruptions is 2).

- If an interruption occurs for more than one day due to the same reason, but the days are not consecutive, i.e. there is at least one dosing day in between, then each dose interruption will be counted as a different occurrence (*example: if the actual dose on days 1, 3 and 5, is 750 mg and actual dose on days 2 and 4 is 0mg, and dose interruptions on day 2 and 4 are both due to dosing error, the total number of dose interruptions is 2).*

A dose change is defined as a change in dosing from one record to the next, however a dose interruption will not be counted as a dose change.

Dose reductions are a subset of dose changes where dose changes to higher than protocol planned dose are excluded.

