7.1.3 PK Run-in period

The first 15 patients enrolled will participate in a single-dose PK run-in period. Additional patients may be enrolled in the study with PK run-in period in case PK profiles from some of the enrolled patients are deemed not evaluable due to early discontinuation from the study or due to vomiting events on the day of PK sampling. In order to characterize the pharmacokinetics of LDK378 in Chinese patients, a single-dose PK run-in period of 5 days will be completed. Since the Cycle 1 Day 1 pre-dose PK collection is considered the 120 hours post-dose PK time point of the PK run-in period, if possible, Cycle 1 Day 1 should immediately follow the 5-day PK run-in phase. If a break between Day 5 of the PK run-in period and Day 1 of Cycle 1 occurs, a 120 hour post-dose PK sample should be collected on the 6th day of the PK run-in phase and no pre-dose PK sample should be collected at Cycle 1 Day 1.

For details of assessments during the PK run-in period, refer to [Table 7-4](#).

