2.4 Study design

This is a phase I/II, open-label, multi-center study to assess the PK, safety, tolerability and efficacy of LDK378 in adult Chinese patients with locally advanced or metastatic NSCLC harboring a confirmed ALK rearrangement. Patients must have demonstrated progression during or after crizotinib treatment whether or not previously treated with cytotoxic chemotherapy and have no available ALK-targeted treatment options.

Overall approximately 100 patients will be enrolled in the study. The first 15 enrolled patients will enter a 5-day PK run-in period during the phase I component of this study. They will have PK sampling over 120-hour during the run-in period following a single oral dose at 750 mg. Additional patients may be enrolled in the study with the 5-day PK run-in period in case PK profiles from some of the enrolled patients are deemed not evaluable

The phase II component of the study will start on Cycle 1 Day 1 for all enrolled patients. During this period LDK378 will be given as continuous daily oral dosing at 750 mg QD in 28 -day cycles.

[figure not shown]
Extensive PK assessment will be collected for the first 15 enrolled patients to obtain approximately 12 evaluable full profiles. Sparse PK samples will be collected for the rest of patients. Adverse events will be collected at every visit after informed consent obtained. Laboratory assessment including hematology and blood chemistry will be taken at screening, run-in Day 1 for the first 15 enrolled patients, Day 1, Day 8, Day 15 for cycle 1 and Day 1 for subsequent cycles. Separate ECG monitoring schedules will also be collected for patients with extensive PK assessment and those with sparse assessment.

[figure not shown]
Tumor response will be evaluated every 8 weeks (i.e. every 2 cycles) starting from the first day of treatment with LDK378 until the time of RECIST-defined Progressive disease (PD) by investigator assessment, withdrawal of consent for further follow-up, loss to follow-up or death. This schedule of tumor assessment will continue regardless of dose interruptions. For patients who discontinue treatment in the absence of progression, tumor assessments will continue every 8 weeks until progression of disease, withdrawal of consent for further follow-up, loss to follow-up or death.

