3.1.1.3 Duration of exposure and Intensity

Definitions of duration of exposure, cumulative dose, average daily dose, actual dose intensity (DI), planned dose intensity (PDI), relative dose intensity (RDI), as well as intermediate calculations, include:

- Duration of exposure (days): last date of study drug – first date of study drug + 1 (periods of interruption are not excluded)
- Cumulative dose (mg): total dose of study drug taken by a patient in the study

- Number of dosing days (days): duration of exposure – number of zero dose days
- Average daily dose (mg/day): cumulative dose (mg)/number of dosing days, drug free day(s) in PK run-in period are not counted
- DI (mg/day): cumulative dose (mg)/duration of exposure (days)
- PDI (mg/day): cumulative planned dose (mg) / duration of exposure (days)
- RDI (%): $100 \times DI \text{ (mg/day)} / PDI \text{ (mg/day)}$

The cumulative planned dose is defined as the total planned dose according to the planned dosing schedule during the study treatment exposure. It is therefore calculated as follows: cumulative planned dose (mg) = protocol planned dose of 750 (mg)* duration of exposure.

For the first 15 patients who are planned to receive a single dose during the PK run-in period (of 5 days), and patients receive daily dosing thereafter, the cumulative planned dose is calculated as follows:

Cumulative planned dose (mg) =

- 750 (mg) * (duration of exposure -4), if duration of exposure (day) >5
- 750 (mg), if duration of exposure (day) ≤5

The similar procedure for calculation is applied to calculation of dosing days for the first 15 patients enrolled in the PK run-in period;

Number of dosing days (days) =

- duration of exposure – (number of zero dose days + 4), if duration of exposure (day) >5
- duration of exposure, if duration of exposure (day) ≤5

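### Planned-dose, dosing-day and interruption rules allow for the four drug-free run-in days only in the first 15 patients, although more run-in patients are permitted

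*SAP*

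**What the plan says.** The design does not cap the run-in at 15 patients. Protocol 7.1.3 foresees more when profiles cannot be used; its sentence begins "Additional patients may be enrolled in the study with PK run-in period in case PK profiles from some of the enrolled patients are deemed". SAP 2.4 repeats it: "Additional patients may be enrolled in the study with the 5-day PK run-in period". Neither gives a number.

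Three SAP rules adjust for the four days without drug that follow the single run-in dose:

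- **Cumulative planned dose (3.1.1.3).** The general rule is "cumulative planned dose (mg) = protocol planned dose of 750 (mg)* duration of exposure". The adjusted rule is introduced by "For the first 15 patients who are planned to receive a single dose during the PK run-in period" and reads "750 (mg) * (duration of exposure -4), if duration of exposure (day) >5", or a single 750 mg dose for shorter exposure.
- **Number of dosing days (3.1.1.3).** The general rule is duration minus zero-dose days. For the first 15 run-in patients a further 4 days are subtracted when exposure exceeds 5 days.
- **Interruptions (4.1.6).** Any run of 0 mg days counts. The exemption for the four run-in days starts with "For the first 15 patients who are planned to receive a single dose on the first day of the PK run-in period".

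Nothing in either document extends these adjustments to later run-in patients. The same SAP section does describe planned dose as following the planned schedule, and its average-daily-dose line leaves out run-in drug-free days with no limit to 15 patients.

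**The concern.** A sixteenth or later run-in patient follows the same schedule as the first 15: one 750 mg dose, four days off by design, then daily dosing. Under the literal text that patient falls back on the general rules. Planned dose then includes four doses that nobody scheduled, which conflicts with the SAP's own description of planned dose. Full compliance is reported as under-dosing, and the days off may be reported as an interruption.

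These quantities feed the exposure summaries of SAP 3.2.5: RDI with its categories, the number of patients with interruptions, and the Kaplan–Meier display of time to first interruption. Because the rules are programming specifications, a limit to the first 15 patients can be coded exactly as written.

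**Working it through.** **Inputs.** Daily dose 750 mg; run-in of 5 days with one dose; 28-day cycles (protocol 6.1.1, SAP 2.4). Duration of exposure D is last minus first dosing date plus 1, gaps included (SAP 3.1.1.3). RDI categories are cut at 50, 75, 90 and 110% (SAP 3.2.5). Patients treated: 103 (protocol, Amendment 3 rationale).

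**Reproducing the SAP's adjusted rule.** For D > 5 the schedule contains 1 + (D − 5) = D − 4 doses, so planned dose is 750 × (D − 4). This equals the SAP formula. The adjustment itself is right; only the group it covers is in question.

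**RDI under the literal text.** RDI is dose intensity over planned dose intensity. Both are divided by D, so D cancels and RDI = cumulative dose / cumulative planned dose. For a fully compliant additional run-in patient this is 750(D − 4) / 750D = (D − 4)/D.

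| Exposure | D (days) | Taken (mg) | Literal planned (mg) | Literal RDI | Adjusted RDI |
|---|---|---|---|---|---|
| Run-in + 1 day | 6 | 1,500 | 4,500 | 33.3% | 100% |
| Run-in + 1 cycle | 33 | 21,750 | 24,750 | 87.9% | 100% |
| Run-in + 2 cycles | 61 | 42,750 | 45,750 | 93.4% | 100% |
| Run-in + 6 cycles | 173 | 126,750 | 129,750 | 97.7% | 100% |

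**Categories.** (D − 4)/D < 0.90 exactly when D < 40, and < 0.75 exactly when D < 16. A fully compliant patient is therefore misclassified only with fewer than 40 days of exposure. For a patient with true reductions, the literal RDI is the true RDI times the same factor, so one close to a cut point could drop a category later.

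**A patient with the run-in dose only.** D = 1, planned dose 750 mg, RDI 100%, no interruption. No error arises.

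**Dosing days and interruptions depend on how the days off are recorded.** Take D = 33, where the correct number of dosing days is 29.

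- *Recorded as 0 mg:* the general rule gives 33 − 4 = 29 dosing days, which is correct. The four consecutive days count as one interruption, starting on study day 2, where the correct count is 0.
- *Not recorded as 0 mg:* the general rule gives 33 − 0 = 33 dosing days, four too many. No false interruption arises.

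So one or the other goes wrong, not both. The documents do not settle which. The exemption in 4.1.6 implies that the days would otherwise count. The adjusted dosing-day rule takes off 4 in addition to the zero-dose days, which gives 29 only if the days are not already among them; otherwise it would give 33 − (4 + 4) = 25.

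**Effect on the interruption percentage.** Each affected patient adds at most 1/103 = 0.97 percentage points, and nothing if the patient also has a true interruption. For assumed counts of 1, 3 and 5 additional patients the ceilings are 1.0, 2.9 and 4.9 points.

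**The case against.** The strongest reply is that no affected patient is known to exist. Additional run-in patients were permitted, but no section says that any were enrolled. Recruitment had ended before the detailed interruption rules were added to the SAP in January 2017. SAP 3.2.8 divides the population into the 15 run-in patients and the rest, and the title of protocol Table 7-6 also speaks of 15. On this view the phrase is simply a label for the run-in cohort, and a sensible programmer would apply the rule to everyone on that schedule. That stands as a limit on the practical effect, which may be nil. It does not rescue the wording: SAP 2.4 in the same version still provides for additional run-in patients, and SAP 4.4 shows that the plain term for run-in patients was available.

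A second reply is that the size is small. At the earlier global study's median exposure of 26.9 weeks (protocol 1.2.1.2.1), about 188 days, literal RDI would be 184/188 = 97.9%, in the correct category. That stands too; the error matters mainly for short exposure.

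A reader might also infer that a primary objective is compromised, because safety and tolerability are primary. The documents do not support that. Protocol 10.5.3.5 summarizes tolerability by reductions or interruptions due to an adverse event, and a scheduled day without drug has no such cause.

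**Conclusion.** The three rules are wrong as written, and the point is minor. If at least one additional run-in patient was enrolled and dosed after run-in day 1, the literal text understates that patient's RDI by the factor (D − 4)/D. It also produces either one false interruption or four surplus dosing days, depending on how the days off are recorded. The RDI part follows from arithmetic alone; the interruption part assumes that the drug-free days appear as 0 mg in the dosing record.

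The effect is confined to descriptive exposure summaries: RDI, number of dosing days, interruptions for any reason and time to first interruption. Average daily dose is protected by its own line. AE-driven tolerability, PK and efficacy results do not change.

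Two stronger readings should be resisted. One is that reported exposure tables are in error: the documents never state how many patients took the run-in, and with exactly 15 nothing changes. The other is that every additional run-in patient is affected: one who took only the run-in dose is not.

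**What to change.** In all three rules (planned dose and dosing days in SAP 3.1.1.3, the interruption exemption in SAP 4.1.6), replace the limit to the first 15 patients by *all patients who entered the PK run-in period*. State in the same place whether the drug-free run-in days are recorded as 0 mg, so that they are removed once and only once.

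The cost is a wording edit and a check of the program. It needs no new data, and extending the group changes nothing for the first 15. The sponsor can see at once from enrollment records whether any result is affected. The fixed 4 days would still not cover a longer break before Cycle 1 Day 1, which protocol 7.1.3 foresees; that applies to the first 15 as well and could be handled in the same edit.
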